Statistical Analysis Plan: In-Home Care for Patients with PSP and Related Disorders

NCT03552484

3-18-2019

Outcome ascertainment

Primary outcomes. The EQ5D will be completed at Visits 1-4 for program patients and annually for controls. This scale measures 5 domains of quality of life: *mobility, self care, usual activities, pain/discomfort, anxiety/depression*; each domain is scored from 1 to 5, with higher scores indicating better function. The scale also includes one item measuring overall self-rated health on a visual analogue scale (VAS) from 0 to 100, where 100 is “best health you can imagine”. This generic scale has been studied in PSP and related disorders and is available in an online format, supporting the feasibility of our control group. Change will be assessed in each EQ5D domain and in the VAS between baseline and 1 year. The instrument will also be administered at Visits 2 and 3 to avoid missing data if dyads are lost to follow-up prior to Visit 4. The MCSI will be completed at Visits 1-4 for caregivers, and annually for control caregivers. This scale is scored from 0-72, with 20-29 indicating moderate strain, 30 or higher indicating severe strain. MCSI scores will be evaluated as both continuous and categorical variables.

Demographics and confounders. include *race, ethnicity, education, insurance*, for patients and caregivers respectively; *living situation* (home or nursing facility), *diagnosis, diagnosis duration* (from year of onset or diagnosis, if onset unknown), and *comorbidities*.

Other variables of interest. The following items will be evaluated in program patients only: *hallucinations, motor severity (UPDRS, HY), and satisfaction* with the program (*Client Satisfaction Index-Short Form, CSI-SF*) administered to patients and caregivers.

Power calculation: Based on pilot recruitment, we anticipate enrolling 20 patients in home visits over 12 months, with a 15% drop out rate, yielding 17 patients at 12 months. We anticipate enrolling 100 control patients and 60 control caregivers, with a 20% drop out rate, yielding 80 patient and 48 caregiver controls. To detect a minimum clinically important difference of 6.5-8.0 in the EQ5D VAS, assuming a baseline mean of 37, standard deviation of 18, power of 0.80 and two-sided alpha of 0.05, we would require 42-63 patients.

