Data management: The primary data will be entered into a HIPAA-compliant database (**REDCap**), with quarterly audits for fidelity. Data will be exported to Stata 14 for analysis.

Data analysis:

Descriptive statistics. We will describe the demographics, disease characteristics, QoL, and caregiver strain at baseline in patients and caregivers. Categorical variables will be summarized by frequencies and percentages. Continuous variables will be assessed for normality and summarized by mean and standard deviation, or median and interquartile range. Adequacy of matching will be evaluated using chi-square and *t*-tests.

Bivariate analyses. Change in EQ5D subscores and VAS over 1 year will be compared between groups, stratified by diagnosis, by two-sample *t*-test or nonparametric Wilcoxon rank sum test. If a subject dies or is lost to follow-up, the last values of the EQ5D will be carried forward. We will analyze the association with change in EQ5D for each demographic, confounder, and covariate via chi square or multivariate ANOVA, as appropriate. We will compare change in MCSI over 1 year by group, stratified by diagnosis; if lost to follow-up, the last MCSI value will be carried forward.

Multivariable analyses. We will construct a linear regression model with change in EQ5D domains and VAS as sequential dependent variables, and treatment status as the primary independent variable, stratifying by diagnosis. We will build complex models to assess the contributions of each significant covariate. Model building will include manual stepwise, backward elimination checking for multicollinearity and confounding. We will construct similar models wherein MCSI change is the dependent variable.

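### Carry-forward records every control without a 12-month survey as exactly unchanged, treats home-visit losses differently and gives dead patients a living EQ5D score; the bias is systematic but small

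*SAP*

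**What the plan says.** - **Imputation rule** (SAP, Bivariate analyses). For quality of life: "If a subject dies or is lost to follow-up, the last values of the EQ5D will be carried forward". For caregiver strain: "if lost to follow-up, the last MCSI value will be carried forward". The second sentence does not mention death.
- **Measurement schedule** (SAP, Primary outcomes). "The EQ5D will be completed at Visits 1-4 for program patients and annually for controls"; the MCSI follows the same pattern. The reason given for the intermediate visits is: "The instrument will also be administered at Visits 2 and 3 to avoid missing data if dyads are lost" before Visit 4.
- **Controls** (Protocol III, usual care paragraph, and Appendix A). One survey at baseline and one at 12 months, with nothing between. Protocol I.c has controls surveyed yearly for two years, but a survey after month 12 supplies no earlier value to carry.
- **Use of the change score.** "Change in EQ5D subscores and VAS over 1 year will be compared between groups, stratified by diagnosis", by t-test or rank-sum test. Then, under Multivariable analyses: "We will construct a linear regression model with change in EQ5D domains and VAS as sequential dependent variables". That paragraph has no missing-data rule of its own.
- **Numbers.** In the SAP's Power calculation, "we anticipate enrolling 20 patients in home visits over 12 months, with a 15% drop out rate", with 100 control patients and 60 control caregivers losing 20%. Protocol II.a plans 25 home-visit and 60 control patients. These enrolment figures conflict and must be reconciled.

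Neither document plans a missing-data sensitivity analysis or handles death separately.

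**The concern.** One sentence acts as two rules. In the control arm, carrying the last value forward always means carrying the baseline, so a lost control counts as a patient who did not change. In the home-visit arm it may mean a value from about month 4 or month 8. The two arms' mean changes are therefore pulled towards zero by different amounts, and part of the between-group difference in a primary outcome reflects how each arm was lost and measured rather than the program.

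For the EQ5D the rule also turns a death into a living score: no change for a control or for a home-visit patient who dies before Visit 2, and the last living value for later home-visit deaths. In a progressive disease, recording death as stability is hard to defend.

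**Working it through.** **The plan's own retention figures.** 20 × 0.85 = 17; 100 × 0.80 = 80; 60 × 0.80 = 48. All three match the SAP. The patients given exactly zero change are 100 - 80 = 20 controls, and 60 - 48 = 12 control caregivers on the MCSI. At the protocol's 60 control patients, 0.20 × 60 = 12.

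**Bias formula for the VAS.** Inputs from the documents: loss of 15% and 20% (SAP) and visits 4 months apart (Protocol I.c and III). Assumed: linear decline over the year of Dh (home-visit) and Dc (control), and losses unrelated to outcome. Let f be the share of the year's decline already seen at the last visit: 0, 1/3 or 2/3 after Visit 1, 2 or 3.

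- Home-visit mean change after carry-forward: -(0.85 + 0.15f)Dh
- Control mean change after carry-forward: -0.80Dc
- Bias in home-visit minus control: 0.15(1 - f)Dh - 0.20Dc

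**Equal decline, Dh = Dc = D.** Bias = -0.05D - 0.15fD. The first term comes from unequal loss (15% v 20%). The second comes from the visit schedule and runs from 0 to -0.10D. The total is -0.05D to -0.15D: at D = 8, -0.4, -0.8 or -1.2; over D = 5 to 12, from -0.25 to -1.8. Protocol I.c also calls the visits quarterly; f = 1/4 and 1/2 give -0.0875D and -0.125D, inside the range.

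**True benefit of 8.0.**

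| Home-visit change | Control change | Bias | Reported |
|---|---|---|---|
| 0 | -8 | -0.20 × 8 = -1.6 | 6.4 |
| +4 | -4 | -0.6(1 - f) - 0.8 = -1.4 to -1.0 | 6.6 to 7.0 |

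**Direction.** The sign changes when Dh/Dc exceeds 0.20/(0.15(1 - f)), that is 1.33, 2 or 4 for f = 0, 1/3, 2/3.

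**Scale.** With SD 18 (SAP) and a baseline-to-12-month correlation of 0.5 (assumed), the SD of change is 18 × √(2 × 0.5) = 18. With complete data the SD of the difference would be 18 × √(1/20 + 1/100) = 4.41, or 18 × √(1/25 + 1/60) = 4.28. In 6,000 simulated trials with carry-forward it was 4.25 and 4.07. A bias of 0.4 to 1.2 is thus 0.1 to 0.3 of a sampling SD.

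**Domains and MCSI.** On a five-level domain, the share of controls recorded as unchanged rises from u to 0.80u + 0.20, for example from 50% to 60%. For the MCSI, equal worsening E gives +0.05E to +0.15E against the program if home-visit caregivers are also lost at 15% (assumed): 0.15 to 1.35 points for E = 3 to 9.

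**Death.** With D = 8 and SD of change 18, a dead control scored as unchanged ranks above Φ(8/18) = 67% of surviving controls. As an illustration, assume 5% home-visit and 10% control deaths and survivors who do not differ. With death ranked worst, the probability that a home-visit patient does better is 0.95 × 0.90 × 0.5 + 0.95 × 0.10 + 0.05 × 0.10 × 0.5 = 0.525. With carry-forward it is 0.488. With the death rates swapped, the values are 0.475 and 0.501. These shifts are 0.4 to 0.5 of the null standard error (0.071 at 20 v 100).

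**The case against.** - **Small and exploratory.** Protocol II.a calls the study exploratory, and the bias is a fraction of the sampling error. This stands. By root mean squared error, carry-forward is no worse than a mixed model: 4.33 v 4.70 with equal decline and 4.58 v 4.76 at a true benefit of 8.0 (20 v 100).
- **The schedule is not the main driver.** A reader might infer that the extra home visits turn a true 8.0 into 6.4, below the SAP's lower important difference of 6.5. The documents do not support that. The 6.4 arises because lost controls are set to zero, and it would be the same if home-visit patients had only two measurements. It also assumes home-visit patients do not improve, whereas hypothesis 1 in Protocol I.a says they will. Moreover, 6.5 is an input to the power calculation, not a decision threshold.
- **A mixed model is not automatically valid.** This stands too. When correlation decays with time between visits, a random-intercept model with model-based errors rejected 7.2% (20 v 100) and 8.9% (25 v 60) of simulated trials with no effect, against 5.5% and 5.1% for carry-forward with Welch's test. In a further simulation (500 runs per scenario), its intervals covered about 91-94% with model-based errors and 93-96% with patient-clustered robust errors. Its mean stayed near the truth, while carry-forward reported about 6.4-6.5 for a true 8.0.
- **Informative loss.** If drop-outs decline twice as fast (D = 8, 20 v 100), the model's bias is -0.5 when this holds in both arms (carry-forward -1.6), -1.7 when in controls only (-2.4), and +1.0 when in home-visit patients only (about 0). The model is a partial cure.
- **The regression may use the imputed score.** The same change variable is named, so this is a natural reading. If it is not imputed there, the comparison would use 120 patients and the regression 97. The SAP should say which.

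**Conclusion.** The concern holds. That every lost control is given zero change, and that the dead receive a living EQ5D score, follows from the text without any assumption. The size of the bias does rest on assumptions: the SAP's loss rates, linear decline, loss unrelated to outcome, and a yearly decline that the documents do not give. On that basis it is -0.05D to -0.15D with equal decline, of which 0.05D is due to unequal loss and 0 to 0.10D to the schedule. A true 8.0 would be reported as 6.4 to 7.0 in the two benefit scenarios above.

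Three stronger readings are not supported. No conclusion is shown to reverse. The rule is not reliably conservative: home-visit patients must be homebound and controls need independent computer access (Protocol II.e), so decline may differ by arm and the sign may change. Nor are deaths missing from study records, since Protocol III.b reviews the status of all subjects; they are blended into the score. The simulated figures ignore the planned stratification by diagnosis.

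**What to change.** In the SAP's data analysis section:

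1. Replace carry-forward as the primary method for VAS and MCSI with a likelihood-based repeated-measures model on all observed values (home-visit Visits 1-4, control baseline and 12 months), with categorical visit and arm by visit. Report the 12-month contrast with patient-clustered robust standard errors, or a covariance that lets correlation decay with time; do not rely on model-based random-intercept errors alone.
2. Use the same observed data, with no carried values, for the five domains and in the multivariable models.
3. Impute no EQ5D score after death. Report known deaths by arm, and add a sensitivity analysis ranking known deaths worst, using the Wilcoxon test already named.
4. Add one delta-adjusted sensitivity analysis by arm. Shifting missing VAS values by 0 to -8 moves the contrast by at most 0.20 × 8 = 1.6 points (controls) or 0.15 × 8 = 1.2 (home-visit).
5. Keep carry-forward only as a sensitivity analysis.

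**Cost.** SAP wording and a few extra analyses of data already collected. In simulation with a random-intercept model, the SD of the contrast rose from 4.25 to 4.70 (11%) at 20 v 100 and from 4.07 to 4.59 (13%) at 25 v 60, and root mean squared error did not fall. What is bought is removal of the arm-dependent bias when loss is not informative. Tracing the vital status of controls who do not answer emails would be a new procedure and is not required for this change.

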##### II.d. Racial and Ethnic Origin

There will be no exclusion of subjects based on racial or ethnic characteristics. Study demographics are expected to match those of the population from which it was drawn. However, subjects must be fluent in English to participate in the Home Visit Program due to the general lack of appropriately translated

neurological and neuropsychological assessments and appropriate normative comparison samples. These factors are critical for accurate administration, scoring, and interpretation of neurological and neuropsychological test data.

II.e. Inclusion Criteria for All Subjects:

1. Each subject must be 40 years of age or older. A subject may be of either gender, any race/ethnicity.
2. Subjects will be those diagnosed with progressive supranuclear palsy, multiple system atrophy, corticobasal syndrome, Dementia with Lewy Bodies (DLB), or atypical parkinsonism without mention of idiopathic Parkinson's disease.
3. English speaking.

a. **Additional Inclusion Criteria For Home Visit Arm:**

- i. Each subject must *either* 1) be willing and able to provide written, informed consent for the study, and for whom capacity to consent will be assessed using the "Additional Inclusion Criteria for Home Visit Arm" document, or 2) if unable to provide informed consent due to lack of capacity, a caregiver is able to provide informed consent *and* the subject provides assent to participation.
- ii. Subjects must be homebound according to the Medicare definition: "Leaving your home isn't recommended because of your condition; your condition keeps you from leaving home without help (such as using a wheelchair or walker, needing special transportation, or getting help from another person); leaving home takes a considerable and taxing effort." (<http://www.medicare.gov/pubs/pdf/10969.pdf>)
- iii. Subjects reside in Chicago at the time of Visit 1.
- iv. The Subject must reside independently at the time of Visit 1.
- v. Subjects have one or more of the following criteria:
  - Fluctuation
  - Multi-morbidity
  - Mismanages medication
  - Cognitive impairment
  - Symptoms of depression and/or anxiety
  - High risk for re-hospitalization
  - High risk for nursing facility admission
  - Suspected elder abuse
  - Recent history of increased falls in home
  - Caregiver burnout suspected
- vi. Ability to participate in the research study as deemed by the Principal Investigator.

b. **Additional Inclusion Criteria for Usual Care Arm:**

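### One-year change is compared between arms with different entry criteria and no baseline EQ5D or MCSI term, so baseline imbalance could look like benefit, or hide it

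*SAP*

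**What the plan says.** **Entry criteria.** Protocol II.e requires home-visit patients to meet the Medicare homebound definition and at least one of ten risk items. Two of the ten are "Symptoms of depression and/or anxiety" and "Caregiver burnout suspected". The extra criteria for usual care are an internet-connected computer, an email address and the ability to give one's own consent. None concerns mobility, mood or caregiver strain.

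**Outcomes.** The SAP (Outcome ascertainment) makes the EQ5D and MCSI primary. Both are scheduled at Visits 1–4 in the home-visit arm and annually in controls. Each EQ5D domain is bounded from 1 to 5.

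**Analysis.** Under Bivariate analyses, one-year change is compared by two-sample t-test or Wilcoxon test. The Multivariable analyses paragraph then sets out the regression: "We will construct a linear regression model with change in EQ5D domains and VAS as sequential dependent variables, and treatment status as the primary independent". These models are stratified by diagnosis, with covariates chosen by stepwise and backward elimination. MCSI change is modelled in the same way. The confounder list covers race, ethnicity, education, insurance and living situation, and then runs "home or nursing facility), *diagnosis, diagnosis duration* (from year of onset or diagnosis, if onset unknown), and *comorbidities". Baseline quality of life and strain appear only under Descriptive statistics.

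**The concern.** The home-visit arm enters through criteria related to what is later measured. Homebound status overlaps EQ5D mobility and, less directly, self-care and usual activities. Depression or anxiety symptoms overlap an EQ5D domain, and suspected burnout overlaps the MCSI. If this makes the arms differ at baseline, two artefacts could enter the comparison of change:

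- **Regression to the mean.** A state that was temporarily bad at entry tends to ease within a year without any program. This is most plausible for anxiety/depression and the MCSI.
- **Worst-level limit.** A patient already at the worst level of a domain cannot decline on it, while a control at a better level can. This is most plausible for the mobility-type domains.

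Either could yield better EQ5D change or less worsening of strain with no program effect, which is the pattern hypotheses 1 and 2 in Protocol I.a predict. An opposite bias is also possible: a sicker arm may truly decline faster. As planned, the analysis would not show a reader how far the result depends on the baseline difference. This is separate from UPDRS and HY being recorded in program patients only, because baseline EQ5D and MCSI are planned in both arms.

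**Working it through.** **The plan's own figure.** The SAP states its target as follows: "To detect a minimum clinically important difference of 6.5-8.0 in the EQ5D VAS". It gives the inputs and the result as follows: "assuming a baseline mean of 37, standard deviation of 18, power of 0.80 and two-sided alpha of 0.05, we would require 42-63 patients". The one-sample formula n = (1.960 + 0.842)² × 18² / δ² gives 7.849 × 324 / 64 = 39.7 for δ = 8.0 and 7.849 × 324 / 42.25 = 60.2 for δ = 6.5. With the t-distribution these become 41.7 and 62.1, so 42 and 63 reproduce. This point does not depend on that figure; it supplies only the SD of 18, read here as the SD of the score.

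**Not in the documents:** the test-retest correlation r, the baseline gap g between arms, and the share of each arm at the worst level. What follows is illustration.

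**Regression to the mean.** Assume equal variances at both times, no program effect, and an observed home-visit mean g below the control mean because of transient selection. The expected spurious gain is (1 − r) × g. With g = 9 (0.5 × 18):
- r = 0.8: 0.2 × 9 = 1.8 points
- r = 0.5: 0.5 × 9 = 4.5 points

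**How the two models relate.** With within-arm slope r, the baseline-adjusted contrast equals the raw change contrast minus (1 − r) × g.
- Gap wholly transient: raw change is biased by +(1 − r)g and the adjusted estimate by 0.
- Gap wholly a stable trait: raw change is biased by 0 and the adjusted estimate by −(1 − r)g.

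**Simulation with no program effect** (3,000 runs per setting, SD 18). Arm sizes are 17 v 80 from the SAP or 25 v 60 from Protocol II.a. The SAP's home-visit figure is stated as "we anticipate enrolling 20 patients in home visits over 12 months, with a 15% drop out rate, yielding 17 patients at 12 months"; its control figure, after dropout, is stated as "yielding 80 patient and 48 caregiver controls".

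| Source of gap | Gap | r | Raw-change bias | Adjusted bias |
|---|---|---|---|---|
| Selection on the measured baseline (both arm sizes) | 0.3–1.0 SD | 0.5, 0.7 | +1.7 to +9.5 points; 7–59% false positives | within 0.1 point; 4–6% false positives |
| Stable trait (25 v 60) | 0.5–1.0 SD | 0.5, 0.7 | about 0 | −2.6 to −8.9 points |

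**Worst-level limit.** If a proportion p of those able to decline lose one level, and shares f_h and f_c start at the worst level, the spurious difference is p × (f_h − f_c). With assumed values: 0.3 × (0.30 − 0.10) = 0.06 levels, up to 0.5 × (0.50 − 0.05) = 0.225 levels. A simulation with more extreme shares (50–69% v 2–7%, r = 0.7, equal underlying decline) gave raw differences of 0.17–0.65 levels in favour of the program. A linear baseline term turned these into 0.13–0.54 levels against it.

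**The case against.** **No criterion uses an outcome score.** A reader might infer that the home-visit arm is selected on the outcomes themselves. The documents do not support that. The two overlapping items are two of ten alternatives, and a patient may enter on multi-morbidity or falls alone. How many enter through the overlapping items is unknown. This stands.

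**Homebound status is largely lasting.** It is the only mandatory overlapping criterion, and regression to the mean needs a temporary deviation. This stands for the mobility-type domains, where the worst-level limit is the main route. Even there, the homebound definition can be met by using a walker, and patients must live independently at Visit 1, so a large share at the worst level is a guess.

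**The VAS illustration may mislead.** A reader might set 1.8–4.5 points against the SAP's 6.5–8.0 important difference and treat the ratio as the expected bias. No criterion selects on the VAS, and both g and r are assumed. The figures show scale only.

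**The direction is not settled.** Faster true decline in the home-visit arm would work against the program. Controls recruited through support groups and social media may also enrol at a bad time and regress. This stands.

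**Adjustment is not neutral.** If the gap is a stable trait, the adjusted estimate can err against the program by about one minimum important difference. It cannot simply replace the change analysis.

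The study is described as exploratory, and the SAP does not forbid a baseline term. But none is named, and backward elimination does not guarantee one.

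**Conclusion.** The concern holds in a limited form. The entry criteria differ between arms in ways related to the outcomes, change is the only outcome form analysed, and no baseline EQ5D or MCSI score is specified in any model. With no program effect, this could produce an apparent benefit, but it need not: bias in the other direction is also possible. The size cannot be stated from the documents. The 1.8–4.5 points rest on an assumed 9-point observed gap due to transient selection, SD 18 and r of 0.5–0.8.

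A reader might go further and require both estimates to point the same way before any benefit is claimed. The material does not justify that rule, because the adjusted model could hide a real effect when the gap is a stable trait. Nor is there a sound basis for an analysis that drops patients who qualified only by the burnout or mood item. Neither document says that the qualifying items are recorded, and the subset would probably be very small.

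**What to change.** In the SAP, Data analysis, Multivariable analyses:

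1. For each outcome, pre-specify a second model that forces in the baseline value of the same scale and exempts it from backward elimination: baseline VAS for VAS change, baseline domain level for each domain, and baseline MCSI for MCSI change. State in advance how the term enters.
2. Report this model beside the unadjusted change comparison.
3. Report baseline distributions by arm, with the share at the worst level of each EQ5D domain.
4. State that the two estimates rest on different assumptions in a non-randomised comparison, and that adjustment can err against the program if the gap is a stable trait. If they disagree, describe the result as sensitive to baseline imbalance rather than as evidence of benefit.

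**Cost.** One extra model per outcome: 5 domains + VAS + continuous MCSI = 7, using scores already planned in both arms. A linear term uses one parameter; a five-level category uses up to four, which matters with 17–25 home-visit patients split by diagnosis. The conclusion may become more cautious.

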#### Characteristics of the Research Population

##### II.a. Number of Subjects

Total Number of Subjects in Home Visit and Usual Care arms: 85

Number of Subjects in Home Visit Arm: 25 subjects with Progressive supranuclear palsy, multiple system atrophy, corticobasal syndrome, or atypical parkinsonism. Participation in the home visit arm neither requires nor prohibits participation in the survey pilot phase.

Number of Subjects in Usual Care Arm: 60 subjects with Progressive supranuclear palsy, multiple system atrophy, corticobasal syndrome, or non-idiopathic PD atypical parkinsonism. Participation in the usual care arm neither requires nor prohibits participation in the survey pilot phase.

This is an exploratory study; no power analysis was conducted. The number of home visit subjects was projected based on recruitment to pilot work at NYU and discussions with Rush colleagues regarding feasibility. The number of control subjects was based on discussions with CurePSP senior staff regarding the size of their support group and social media-connected networks.

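### With about 17 home-visit patients against 80 controls, the SAP's t-test and regression make no allowance for unequal spread of change; naming Welch and HC3 for the overall comparison is a cheap safeguard

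*SAP*

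**What the plan says.** Under Bivariate analyses, the SAP compares change in the EQ5D domains and VAS between groups, stratified by diagnosis, using a two-sample t-test or a "nonparametric Wilcoxon rank sum test". Under Multivariable analyses it says: "We will construct a linear regression model with change in EQ5D domains and VAS as sequential dependent variables". Treatment status is the main predictor, diagnosis is again a stratifier, and similar models are planned for MCSI change.

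The arm sizes are in the SAP's Power calculation: "we anticipate enrolling 20 patients in home visits over 12 months, with a 15% drop out rate, yielding 17 patients at 12 months" for home visits, and for controls "We anticipate enrolling 100 control patients and 60 control caregivers", "with a 20% drop out rate, yielding 80 patient and 48 caregiver controls". Protocol section II.a has a different split, 25 and 60: "Total Number of Subjects in Home Visit and Usual Care arms: 85".

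Neither document mentions a Welch or other unequal-variance test, robust standard errors or a check of equal variance. The only distributional check is for normality. The only SD is 18, given alongside the baseline mean; no SD of change is given for either arm.

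**The concern.** A pooled t-test, and the equivalent least-squares regression on a treatment indicator, use one variance for both arms. With equal arms this does little harm. At 80/17 = 4.7 to 1, the large arm dominates the pooled variance while the small arm dominates the true uncertainty of the difference. If the small arm is more variable, the standard error is too small and false positives rise. If it is less variable, the test is needlessly conservative.

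The documents give reasons not to take equal spread for granted:

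- Only home-visit patients must be homebound and have at least one listed risk item, while controls need independent internet access (protocol, II.e).
- Home-visit patients are interviewed, while controls complete the survey online themselves (protocol, III).
- Carry-forward acts differently by arm. Controls are measured annually, so a control lost before the one-year survey has a change of exactly zero. A home-visit patient lost later may carry forward a Visit 2 or 3 value.

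**Working it through.** **The plan's own figures.** 20 × 0.85 = 17 home-visit patients; 100 × 0.80 = 80 control patients; 60 × 0.80 = 48 control caregivers. All three agree with the SAP. The stated requirement of 42-63 patients reproduces exactly as a one-sample (paired) t-test calculation with SD 18, so it contains no assumption about the spread of change in each arm.

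**Input not in the documents.** r = SD of change in the home-visit arm divided by SD of change in controls. It is assumed, and shown over a range.

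**Standard errors at 17 v 80, in units of the control SD.**

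- Pooled: √[(16r² + 79)/95] × √(1/17 + 1/80)
- True: √(r²/17 + 1/80)

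For r = 1.5 the pooled value is √(115/95) × 0.2671 = 0.294 and the true value is √(0.1324 + 0.0125) = 0.381. The ratio is 0.77, so the nominal critical value of 1.985 acts like 1.985 × 0.77 = 1.53, which corresponds to a two-sided error of roughly 13%.

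**Simulated type I error at nominal 5%** (normal changes, equal means; 200,000 runs per setting, 60,000 for r = 0.75):

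| r (assumed) | Pooled SE / true SE, 17 v 80 | Pooled test, 17 v 80 | Pooled test, 25 v 60 |
|---|---|---|---|
| 0.75 | 1.20 | 1.9% | 2.8% |
| 1.0 | 1.00 | 5.0% | 4.9% |
| 1.25 | 0.86 | 8.9% | 7.3% |
| 1.5 | 0.77 | 12.9% | 9.7% |
| 2.0 | 0.66 | 19.5% | 12.9% |

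At 17 v 80, for r from 0.5 to 2.0, Welch stays at 5.0-5.1% and HC3 at 4.9-5.6%. At r = 1.5 a nominal 95% interval from the pooled model covers 87.1%. For MCSI, assuming 17 home-visit caregivers against 48, the pooled test gives 7.7% at r = 1.25 and 10.3% at 1.5.

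**Wilcoxon at 17 v 80.** It gives 1.3% at r = 0.5, 8.8% at 1.5 and 11.0% at 2.0. It moves in the same direction as the pooled test and is not a cure.

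**Spread created by carry-forward alone.** Take 20 v 100 analysed, true SD 18 in both arms, mean change zero, and 20 of 100 controls fixed at zero.

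- Control SD becomes √0.80 = 0.894 of its true value.
- With no home-visit zeros, r = 1/0.894 = 1.12. With all 3 home-visit dropouts at zero, r = √(0.85/0.80) = 1.03.
- Pooled type I error with 0, 1, 2 or 3 home-visit zeros is 7.0%, 6.3%, 5.8% or 5.5%.

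**Cost when spreads are equal (17 v 80, SD 18).** The expected 95% half-width on the VAS is 9.54 pooled and 9.94 Welch; 9.94/9.54 = 1.042. Power falls from 0.269 to 0.257 for 6.5 points and from 0.377 to 0.359 for 8.0 points.

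**Small diagnosis strata.** Protocol II.e lists five diagnostic categories. An equal five-way split is an assumption made only for illustration: 20 v 100 gives 4 v 20, and 17 v 80 gives about 3 v 16. With equal SDs:

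| Stratum | Pooled | Welch | HC3 | Welch CI v pooled |
|---|---|---|---|---|
| 4 v 20 | 5.2% | about 6% | about 7% | about 24% wider |
| 3 v 16 | 4.9% | about 7% | about 8% | about 45% wider |

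**The case against.** The strongest reply is that the SAP makes no error here. It does not say pooled or ordinary least squares. Welch is itself a two-sample t-test, and robust standard errors are an option on a linear regression. A reader might infer that the SAP's p-values and confidence intervals are wrong. The documents do not support that: the variance method is unstated, no SD of change is given by arm, and the SAP does not mention confidence intervals. Selecting homebound patients could narrow the spread of change as easily as widen it. All of this stands. What remains is an open choice whose default reading is fragile at these arm sizes.

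Second, the only excess tied to the SAP's own rules is about 5.5-7%. Because carry-forward keeps dropouts in the analysis, 20 v 100 may describe the analysed set better than 17 v 80. That also stands, though 5 to 1 is no better balanced than 4.7 to 1.

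Third, a reader might infer that Welch and HC3 hold 5% in every planned analysis at negligible cost. They do not. The SAP does not say whether stratifying by diagnosis means separate analyses or adjustment. In separate small strata with equal spreads, the two methods exceed 5% while the pooled test does not. This limits the remedy to the overall comparison.

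Fourth, protocol II.a calls the study exploratory. Non-randomised arms, stepwise covariate selection and several outcomes with no stated multiplicity control are larger threats. That bears on priority. It is not a reason to leave the standard error dependent on an unsupported assumption when two sentences would settle the matter.

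**Conclusion.** The point holds as a worthwhile, low-cost improvement. It is not a demonstrated error. Under the default pooled and least-squares reading at 17 v 80, type I error is about 9% if r = 1.25, 13% if r = 1.5 and 2% if r = 0.75; at 25 v 60 the departures are smaller. Carry-forward with equal true SDs gives about 5.5-7%.

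These figures rest on normally distributed changes, on assumed SD ratios, and on the 20% and 15% dropout rates in the SAP. The HC3 figures come from a model with a treatment indicator only; a diagnosis-adjusted model was not simulated.

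**What to change.** In the SAP's Data analysis section:

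1. Under Bivariate analyses, state that the overall comparison of mean change uses the Welch t-test, with no preliminary test of variances.
2. Under Multivariable analyses, state that the overall, diagnosis-adjusted models for EQ5D and MCSI change use HC3 standard errors.
3. Say whether stratification by diagnosis means adjustment or separate analyses. Where strata are analysed separately and are small, report them descriptively and do not apply Welch or HC3 tests to them.

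The change needs a few SAP sentences and software options, with no new data, visits or patients. The statistical price is a confidence interval about 4-5% wider for the overall comparison if the two spreads turn out equal, with a power loss of one to two percentage points.
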